3.3.5. Imputation of Incomplete Dates

An incomplete date is any date for which either the day, month, or year is unknown, but at least one field is known. An incomplete date occurs when the exact date an event occurred or ended cannot be obtained from a subject. For many of the analyses, a complete date is necessary in order to determine if the event should be included in the analysis (ie, if the event is treatment-emergent) or to establish the duration of an event. In such cases, incomplete dates will be imputed.

For purposes of imputation, all events with an incomplete end date are assumed to have ended on or before the day the form was completed. In an effort to minimize bias, the project statistician will impute incomplete start dates in a systematic, but reasonable manner. For diary data, missing dates will be imputed based on the nominal visit day relative to Day 1. For other data, if the month/year is the same as the Day 1 month/year then the date will be set to the date of Day 1. In other cases, missing days will be imputed as the day component of Day 1; missing months/years will be imputed as the month/year of Day 1.

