#### **10.1.2.5. Day 14 (End of Study)**

The Day 14 assessments will be performed as a clinic visit. The following procedures/assessments will be performed on Day 14 (+ 3 days) or at the time of early withdrawal, where possible:

- Measure vital signs (blood pressure, pulse rate, and respiration rate)
- Measure and record oral body temperature
- Perform a urine or serum pregnancy test (non-pregnant females of childbearing potential only)
- Conduct an assessment for the presence of possible IRC; if an IRC is suspected, a targeted physical exam should be conducted to confirm the absence or presence of the IRC
- Review the subject diary for completeness
- Collect a bilateral adequate nasal swab specimen for viral culture, quantitative PCR assay and susceptibility to neuraminidase inhibitors.
- Review and record concomitant medications
- If Day 7 labs are, in the opinion of the investigator, significantly abnormal or significantly changed from baseline, collect blood specimen for clinical chemistry and/or clinical hematology tests as specified in Sections [11.2.1](#) and [11.2.2](#) and a serum sample for future influenza antibody analysis.
- If Day 7 urinalysis is, in the opinion of the investigator, significantly abnormal or significantly changed from baseline, collect urine for urinalysis
- Review and record AEs

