- 7 If an influenza related complication (IRC) is suspected the subject will be instructed to return to the clinic as appropriate to confirm the presence or absence of IRCs.
- 8 A single serum specimen will be collected, where possible, pre-dose on Day 1, Day 3 and on Day 7 for analysis of influenza antibody titers.
- 9 Adverse events are to be collected from the time of informed consent through the follow-up period ending on Day 14.

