Any event reported on the CRF that occurs on or after the initiation of study drug and not more than 14 days after the last dose of study medication is considered treatment-emergent.

Additionally, it is assumed that an AE which was reported to have started on Day 1 without an associated onset time may have occurred after the initiation of study drug. Hence, AEs occurring on Day 1 with no associated onset time are assumed to be treatment-emergent.

Treatment-emergent Laboratory Abnormalities

A treatment-emergent laboratory abnormality is defined as an increase of at least one toxicity grade from the baseline assessment at any post baseline visit up to and including 14 days after the last dose date of study drug. If no assessment is available at baseline, the screening assessment will be used to assign the baseline toxicity grade. If the relevant baseline and screening assessments are missing, then any graded abnormality (ie, at least Grade 1) is considered to be treatment-emergent.

Concomitant Medications

Concomitant medications are those medications taken upon or after the initiation of study drug.

Prior Medications

Prior medications are those medications taken prior to the initiation of study drug. Subjects will record all medications they are currently taking.

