5.3. SAFETY

5.3.1. Adverse Events

AEs will be mapped to a Medical Dictionary for Regulatory Activities (MedDRA) version 18.0 preferred term and system organ classification. If a subject experiences multiple events that map to a single preferred term, the greatest severity grade and strongest investigator assessment of relation to study medication will be assigned to the preferred term for the appropriate summaries. Should an event have a missing severity or relationship, it will be classified as having the highest severity and/or strongest relationship to study medication. An overall summary of TEAEs will be generated, showing the number of subjects with at least one AE, SAE, AE related to study drug, AE leading to discontinuation of study, SAE related to study drug, severe or life-threatening AE, and severe or life-threatening AE related to study drug. Summaries of TEAEs will include any AEs reported beginning with the initiation of study drug on Day 1. The occurrence of TEAEs will be summarized by age group using preferred terms, system organ classifications, and severity. Separate summaries of TEAEs, treatment-emergent SAEs, TEAEs related to study drug, events

leading to the discontinuation of study, and events leading to the discontinuation of study drug will be generated by preferred term and system organ classification. TEAEs occurring in $\geq 10\%$ of subjects will be summarized by preferred term. All AEs reported will be listed for individual subjects showing both verbatim and preferred terms. A separate listing of all SAEs will be generated. All AEs that occurred prior to the initiation of study treatment or more than 14 days post-study drug discontinuation will be excluded from the tables but will be included in the listings.

Missing onset dates will be imputed as previously outlined in Section 3.3.5 as required to determine whether AEs were treatment-emergent.

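### SAP 3.3.5 fills a missing adverse event onset day or month from Day 1, so an in-window onset in the following month can never count as treatment-emergent

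*SAP*

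**What the plan says.** SAP 3.3.5 has two branches for non-diary dates. In the first, "if the month/year is the same as the Day 1 month/year then the date will be set to the date of Day 1". The second covers everything else: "In other cases, missing days will be imputed as the day component of Day 1", and "missing months/years will be imputed as the month/year of Day 1".

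SAP 5.3.1 gives this rule its role in the safety analysis: "Missing onset dates will be imputed as previously outlined in Section 3.3.5 as required to determine whether AEs were treatment-emergent". SAP 3.3.8 sets the window: onset on or after the start of study drug and "not more than 14 days after the last dose of study medication is considered treatment-emergent". There is one dose, on Day 1, so the window is dose to dose + 14 days. Under SAP 5.3.1, events outside it are left out of the tables and shown only in listings.

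Three other statements bear on the result:

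- SAP 1.2, footnote 9: "Adverse events are to be collected from the time of informed consent through the follow-up period ending on Day 14".
- Protocol 10.1.2.5: the final assessments "will be performed on Day 14 (+ 3 days) or at the time of early withdrawal".
- SAP 3.3.5 on end dates: "all events with an incomplete end date are assumed to have ended on or before the day the form was completed".

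**The concern.** An onset recorded in the month after dosing is certainly post-dose and may well lie in the window. The second branch nevertheless moves it about a month past the dose, so it is lost from the treatment-emergent tables.

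Elsewhere the plan leans the other way. Same-month partial dates go to Day 1, and SAP 3.3.8 counts Day 1 events without an onset time as emergent. Only next-month onsets are treated against inclusion, and nothing suggests that this was intended.

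Safety is the primary endpoint and is reported through these tables. The hospitalization summary in SAP 5.2.2 is also counted by treatment-emergent event. With about 120 subjects split by age group, one lost event can be visible.

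**Working it through.** The plan gives no figure on this point, so there is none to reproduce. The check applies the rule to the calendar.

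**Inputs.** Window: 0 to 14 days after the dose (SAP 3.3.8, single dose). Dosing dates: the protocol synopsis estimates October 2015 to April 2018. I took 1 October to 30 April in each of the three seasons with equal weight (an assumption), giving 637 dates in 21 calendar months. *Month/year the same* is read as both matching. A missing month is filled with the recorded day kept.

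**Example.** Dose 25 January 2017, onset recorded as February 2017. True in-window days are 1–8 February. The imputed onset is 25 February, 31 days after the dose. If instead day 02 and year 2017 are recorded and the month is missing, the imputed onset is 2 January, before the dose.

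**General result, day missing.** The same day number in the next month is the dose date plus the length of the dosing month, so the gap is 28, 29, 30 or 31 days. That always exceeds 14.

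- The window reaches the next month for the last 14 dosing days of each month: 21 × 14 = 294 dates, and 294/637 = 46.2%.
- Imputed Study Day (gap + 1): Day 29 for 28 dates, Day 30 for 14, Day 31 for 84, Day 32 for 154; total 280.
- The other 14 dates give no real date: 31 October (3), 31 March (3), 30–31 January 2016 (2), and 29–31 January 2017 and 2018 (6).

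**Share of the window affected.** Each month contributes 1 + 2 + … + 14 = 105 in-window next-month dose/onset pairs: 21 × 105 = 2,205 of 637 × 15 = 9,555, or 23.1%. If onsets fall only in the first 7 days, it is 21 × 21 = 441 of 637 × 7 = 4,459, or 9.9%.

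**Current rule on the 2,205 pairs.**

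| Missing field | Emergent | Not emergent |
|---|---|---|
| Day | 0 | 2,016 after the window, 189 undefined |
| Month | 0 | 1,890 pre-dose, 315 after the window |
| Year | 1,890 | 315 pre-dose (December to January) |

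Over the full calendar, without the seasonal restriction (943 dates), the result is the same: 0 of 3,255 with the day missing and 0 of 3,255 with the month missing. If day and month are both missing and the onset is in the dosing year, the rule gives Day 1, which is emergent. The failure therefore concerns one field or the other.

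**Against the plan's own dates.** Study Day 29–32 is 15–18 days after collection ends on Day 14, and 12–15 days after the latest in-window final visit (14 + 3 = Day 17). If the end date is also incomplete and the form was completed by that visit, the event would start after it was assumed to have ended.

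**Events affected.** The documents give neither an adverse event count nor a rate of missing fields. Assuming 120 events (one per subject), the number is 120 × share × missing-day rate:

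| Share in next month | 1% missing | 5% missing | 10% missing |
|---|---|---|---|
| 9.9% | 0.12 | 0.59 | 1.19 |
| 23.1% | 0.28 | 1.38 | 2.77 |

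**The case against.** The strongest objection concerns size. Events are reviewed in clinic on Days 3, 7 and 14, and Protocol 11.1.2 requires complete and prompt recording. Laboratory findings normally carry a specimen date. Influenza symptoms and complications are not adverse events unless serious. Few onset dates should lack a day, fewer still a month or year, and hospitalizations, usually reported as serious events within 24 hours, are the least likely to be poorly dated. All of this stands: the expected count is low, every event remains listed, and no hypothesis is tested.

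A second objection is that imputation applies only as required. Collection ends on Day 14 (dose + 13 days), so a next-month onset collected by then is already known to be in the window. This does not rescue the rule. SAP 3.3.5 calls for a complete date in order to decide emergence, and the partial date alone does not settle the 14-day limit. The final visit may also be as late as Day 17 (dose + 16 days).

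A third is that, if a missing month were filled first, the same-month branch would then reset the date to Day 1 and the event would be emergent. That would overwrite a recorded day, and the SAP does not prescribe that order.

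**Conclusion.** The point holds. For an onset in the month after dosing with only its day missing, the stated rule gives a date outside the window or no date at all, without exception. With only the month missing, the date is also always outside the window, provided the recorded day is kept. With only the year missing, the failure is confined to December-to-January onsets. The same-month branch is not at fault for missing days.

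The exact part rests on the calendar and on reading the month/year match as both matching. The 46.2% is a share of dosing dates, not of events. The 0.1 to 2.8 events rest on the assumed 120 events and 1% to 10% missing days, so zero to a few is the realistic expectation. This is a narrow drafting fault that should be corrected because it gives a wrong classification for the primary endpoint and the correction is cheap.

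**What to change.** Add to SAP 3.3.5, for adverse event onset dates only:

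*Impute the earliest date from the dose date to the dose date + 14 days that agrees with every recorded field. If there is none, impute the agreeing date nearest the dose date.*

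No recorded field is altered and only real dates can result. With the day missing this gives:

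- Day 1 month: Day 1, as now.
- Next month, beginning within 14 days of the dose: its first day, emergent.
- A month beginning later: its first day, not emergent.
- An earlier month: its last day, pre-dose.

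Under this rule all 9,555 in-window pairs are emergent, whichever single field is missing.

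The cost is one sentence and one date derivation, with no new data. The downside is some over-inclusion. With the day missing, 588 of 651 next-month onset days at dose + 15 or + 16 would count as emergent. A truly pre-dose onset in the Day 1 month with its day missing also counts, but it does so under the present rule. With only the month missing, a pre-dose onset would be counted only if it lay at least 14 days before the dose, whereas collection starts at consent, expected on Day 1.

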3.3.6. By Study Visit Displays

When data are collected serially over time, individual data presentations may include by-visit displays. For these presentations, visits will be presented according to the nominal visit as obtained from the CRF or laboratory data. If assessments are collected with multiple dates or times within a given visit, the result closest to the scheduled visit date will be used for summary presentations. If two measurements have the same distance to the expected date, the earlier value will be used. If a subject has multiple non-missing values on the same date, then the last one will be used, as determined by the time collected, if available.

3.3.7. Derived and Transformed Data

TCID₅₀ will be log₁₀ transformed prior to performing the analyses.

3.3.8. Definitions and Terminology

Age

Age will be defined as the age in years at time of signing of informed consent for all subjects.

Confirmed Influenza

A subject will be confirmed as having acute influenza infection if any specimen for assay of influenza A or B antigen by RT-PCR obtained during the study is positive.

Baseline Value

For purposes of analysis, the baseline value is defined as the last value obtained prior to initiation of study drug (eg, the Baseline Pre-Dose value). Should this value be obtained after the injection of study drug, then the most recent value obtained prior to initiation of study drug will be used for the baseline value.

Day 1

Day 1 is the day/time that study drug is initiated.

Study Day

Study Day is defined relative to Baseline (Day 1). Thus, the study day of an event is calculated as:
Study Day = event date – date of Day 1 +1.

Days on Study

Days on Study is the number of days from Day 1 to the date of study completion or early termination as recorded on the Day 14/End of Study/Early Withdrawal CRF.

Days of Subject Diary Completion

Days of Subject Diary Completion is defined as the number of days from Day 1 to the date of last Subject Diary completion. For the purposes of this analysis, the date of last Subject Diary completion is defined as the last date in which the Subject Diary had at least one complete assessment of symptoms recorded.

Alleviation of Symptoms

A subject has Alleviation of Symptoms if all of the assessed symptoms of influenza assessed on his/her subject diary are either absent or are present at no more than mild severity level and at this status for a 21.5 hour period (24 hours less 10%).

Composite Symptom Score

The Composite Symptom Score is defined as the sum of the seven symptoms of influenza (cough, sore throat, stuffy nose, muscle aches, headache, feverishness, fatigue/tired) assessed on a given time point within the subject diary.

Baseline Composite Symptom Score

The Baseline Composite Symptom Score is defined as the sum of the symptoms of influenza recorded by the subject in the diary corresponding to the assessment of a subject's symptoms prior to the initiation of study drug.

Resolution of Fever

A subject has Resolution of Fever if he/she has a temperature < 37.4°C/99.4°F oral and no antipyretic medications have been taken for at least 12 hours. Resolution of Fever is based on information obtained from the individual subject diaries.

Ability to Perform Usual Activities

The ability to perform usual activities is defined as a subject rating of 10 (able to perform all usual activities fully) on the visual analog scale the subject uses to rate his or her current ability to perform usual activities compared with normal ability.

Time to Event

Time to a given event is defined as the number of hours (days) from initiation of earliest study treatment until the event occurs. The unit of measurement will vary based upon the endpoint and its respective schedule of assessment.

Time to Alleviation of Symptoms

Time to Alleviation of Symptoms is the number of hours from initiation of study drug to start of the 21.5 hour period (24 hours less 10%) where all symptoms of influenza are recorded as none or mild.

Change from Baseline

Change from baseline for a given endpoint is defined as the Study Day X value minus the Baseline Value.

Adverse Event (AE)

According to the protocol, an AE is any untoward medical occurrence in a clinical study subject. No causal relationship with the study drug or with the clinical study itself is implied. An AE may be an unfavorable and unintended sign, symptom, syndrome, or illness that develops or worsens during the clinical study. Clinically relevant abnormal results of diagnostic procedures including abnormal laboratory findings (eg, requiring unscheduled diagnostic procedures or treatment measures, or resulting in withdrawal from the study) are considered to be AEs.

AEs may be designated as “nonserious” or “serious” (see Protocol Section 11.1.1.1). Surgical procedures are not AEs but may constitute therapeutic measures for conditions that require surgery. The condition for which the surgery is required is an AE if it occurs or is detected during the study period. Planned surgical measures permitted by the clinical study protocol and the condition(s) leading to these measures are not AEs if the condition(s) was (were) known before the start of study treatment. In the latter case the condition should be reported as medical history.

Assessment of symptoms of influenza will be documented in a Subject Diary and analyzed as a measure of effectiveness of the study treatment. These symptoms will not be reported as AEs unless the symptom(s) worsen to the extent that the outcome fulfills the definition of a serious adverse event (SAE), which then must be recorded as such (see Protocol Section 11.1.1.2).

All AEs will be recorded on the ADVERSE EVENTS CRF.

Treatment-emergent Adverse Events (TEAEs)

Any event reported on the CRF that occurs on or after the initiation of study drug and not more than 14 days after the last dose of study medication is considered treatment-emergent.

Additionally, it is assumed that an AE which was reported to have started on Day 1 without an associated onset time may have occurred after the initiation of study drug. Hence, AEs occurring on Day 1 with no associated onset time are assumed to be treatment-emergent.

Treatment-emergent Laboratory Abnormalities

A treatment-emergent laboratory abnormality is defined as an increase of at least one toxicity grade from the baseline assessment at any post baseline visit up to and including 14 days after the last dose date of study drug. If no assessment is available at baseline, the screening assessment will be used to assign the baseline toxicity grade. If the relevant baseline and screening assessments are missing, then any graded abnormality (ie, at least Grade 1) is considered to be treatment-emergent.

Concomitant Medications

Concomitant medications are those medications taken upon or after the initiation of study drug.

Prior Medications

Prior medications are those medications taken prior to the initiation of study drug. Subjects will record all medications they are currently taking.

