#### 13.8.2. Effectiveness Analyses

Time to resolution of fever, defined as a temperature  $< 99.4^{\circ}\text{F}$  oral with no antipyretic medications taken for at least 12 hours, will be estimated overall and by each age group using the method of Kaplan-Meier. Subjects who do not achieve resolution of fever will be censored at the time of their last assessment.

Time to resolution of influenza symptoms, defined as the time from initiation of study drug until the start of the 21.5-hour period (24 hours- 10%) where all symptoms of influenza are recorded as none or mild, will be estimated overall and for each age group using the method of Kaplan-Meier. Subjects who do not experience alleviation of symptoms will be censored at the time of the last non-missing symptom assessment.

Reduction in viral shedding will be assessed as the change from baseline in  $\log_{10}$  TCID50/mL and RT-PCR, and will be summarized overall, by age group, and by study visit.

Changes in virus susceptibility to neuraminidase inhibitors between virus cultured at Baseline and the last post-treatment sample from which virus can be cultured will be assessed using virology laboratory tests. Virology laboratory tests will include phenotypic characterizations of influenza virus recovered (hemagglutinin and neuraminidase) and viral susceptibility to peramivir, and genotypic analysis of primary virus isolates. These analyses will be presented overall, and separately by age group and viral subtype.

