Up to 3 blood samples will be drawn to obtain plasma samples for drug concentration determinations, where possible, during the following time periods, beginning from the end of dosing until release from the site on the day of dosing:

- One time point immediately following completion of the infusion
- One time point from 30 minutes to 1 hour post-infusion
- One time point from 1 hour to 3 hours post-infusion

AEs and concomitant medications will be monitored at each scheduled visit from the Screening assessment to final study visit. Clinical laboratory investigations (chemistries, hematology, and urinalysis) will be collected at Baseline, Day 7, and Early Withdrawal visits. Safety and tolerability will be evaluated through assessments of AEs, laboratory analyses (clinical chemistry, hematology, and urinalysis), vital signs, and physical examinations at the time points indicated in the schedule of assessments (see Section 1.2).

All subjects or their caregivers will record the following information in a Subject Diary:

- Assessment of the presence and severity of each of 7 symptoms of influenza on a 4-point severity scale (0, absent; 1, mild; 2, moderate; 3, severe) at Screening, then twice daily through Day 13, and prior to the subject's clinic visit on Day 14 or until each symptom is rated as a 0 or 1 for 48 consecutive hours. Diaries will be reviewed at each clinic visit.
- Temperature measurements (oral) will be taken with an electronic thermometer provided by the Sponsor, approximately every 12 hours until temperature normalizes for 48 hours (ie, temperature without antipyretic is $< 37.4^{\circ}\text{C}/99.4^{\circ}\text{F}$ orally for 4 consecutive measurements). With the exception of the Screening/ Baseline measurement, all temperature measurements will be obtained at least 4 hours after, or immediately before, administration of oral acetaminophen or other antipyretic medications, if taken.
- The type, date, and time of medications used for the symptomatic treatment of influenza-related symptoms.
- Assessment of the subject's ability to perform usual activities using a 0 to 10 visual analog scale once daily through Day 14, where 0 = Unable to perform usual activities at all, and 10 = Able to perform all usual activities fully.

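### Resolution of fever is declared on the first sub-threshold diary reading, with no confirmation or rebound rule, while the companion symptom endpoint must be sustained for 21.5 hours

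*SAP*

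**What the plan says.** SAP 3.3.8 gives the definition: "A subject has Resolution of Fever if he/she has a temperature" under 37.4 °C/99.4 °F orally and "no antipyretic medications have been taken for at least 12 hours". The source is the diary: "Resolution of Fever is based on information obtained from the individual subject diaries". Time to event runs "from initiation of earliest study treatment until the event occurs". SAP 5.2.2 repeats the definition and plans Kaplan-Meier estimates by age group and overall. Protocol 13.8.2 has the same rule, "Time to resolution of fever, defined as a temperature" below 99.4 °F "with no antipyretic medications taken for at least 12 hours".

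Two other diary rules matter here.

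- **Symptom endpoint.** In SAP 3.3.8, time to alleviation runs to the "start of the 21.5 hour period (24 hours less 10%) where all symptoms of influenza are recorded as none or mild". It has a required duration and is timed at the start of that period.
- **Temperature recording.** SAP 1.1 has readings taken "approximately every 12 hours until temperature normalizes for 48 hours", spelled out as four consecutive measurements below the same threshold.

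Neither document says what happens when a reading at or above 37.4 °C follows a qualifying one. No output listed in SAP 9 counts return of fever.

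**The concern.** Twice-daily readings can alternate between the low and the high of the daily temperature cycle. A subject whose temperature is falling slowly may drop below 37.4 °C at a low, be above it again 12 hours later, and still be counted as resolved at the first of these readings. The antipyretic condition protects against drug-masked fever. It does not protect against an ordinary dip or a misread thermometer.

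Protocol 9.9.1 ranks fever resolution among the important efficacy endpoints, and SAP 9 gives it tables, a Kaplan-Meier plot, a figure of medians with confidence intervals and a box plot. The study has a single arm, so a rule that shortens the time has no control arm in which to cancel. It goes straight into the reported figure and into any comparison with other studies.

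**Working it through.** The documents give no sample-size, power or effect figure that depends on this definition, so there is nothing to reproduce.

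**Inputs from the documents.** Threshold 37.4 °C and 12 antipyretic-free hours (SAP 3.3.8, 5.2.2; Protocol 13.8.2); readings about every 12 hours (SAP 1.1); 21.5 hours for the symptom endpoint (SAP 3.3.8). With 12-hourly readings, three consecutive ones span 24 hours and so cover 21.5 hours.

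**Step 1: direction.** Every reading that starts a sustained period is also a qualifying single reading. The earliest member of the smaller set cannot precede the earliest member of the larger one. So, where follow-on readings exist, single-reading time ≤ sustained time. This needs no assumption about temperature.

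**Step 2: chance of stopping while still febrile.** Assume that each reading in a still-febrile subject qualifies with probability q, independently. The documents do not give q; 0.02 to 0.20 is my range. With k readings during fever:

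- one-reading rule: 1 − (1 − q)^k
- three in a row, for k from 3 to 6: q³[1 + (k − 3)(1 − q)]

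For example, with q = 0.10 and k = 4: 1 − 0.9⁴ = 0.344, against 0.001 × 1.9 = 0.0019.

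| q | One reading, 48 h of fever (k = 4) | Three, 48 h | One reading, 72 h of fever (k = 6) | Three, 72 h |
|---|---|---|---|---|
| 0.02 | 7.8% | 0.002% | 11.4% | 0.003% |
| 0.05 | 18.5% | 0.02% | 26.5% | 0.05% |
| 0.10 | 34.4% | 0.19% | 46.9% | 0.37% |
| 0.20 | 59.0% | 1.44% | 73.8% | 2.72% |

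A simulation carried this through to medians: 40,000 subjects, exponential fever duration with median 48 h, and no raised readings after true resolution. One-reading against three-reading medians were 48 vs 48 h (q = 0.05), 36 vs 48 h (q = 0.10) and 24 vs 48 h (q = 0.20). With q = 0 they agree.

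**Step 3: slowly falling temperature with a daily swing.** Assumed: start 38.5 °C, fall uniform on 0.2 to 0.6 °C per day, readings every 12 hours, 20,000 subjects per setting. The antipyretic condition is not modelled.

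| Swing; reading SD (°C) | Mean, one reading | Mean, three readings | Gap | Reading ≥ 37.4 °C among next two |
|---|---|---|---|---|
| ±0.10; 0.15 | 75.1 h | 82.0 h | 6.9 h | 25% |
| ±0.25; 0.15 | 67.8 h | 89.2 h | 21.4 h | 66% |
| ±0.10; 0.25 | 71.2 h | 84.3 h | 13.1 h | 38% |
| ±0.25; 0.25 | 64.6 h | 89.1 h | 24.5 h | 65% |

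The gap in medians ranges from 0 to 24 h, partly according to whether the first reading falls at the daily low or high.

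**Step 4: what shrinks the gap.** If temperature falls by 0.6 to 1.2 °C per day, the mean gap drops to about 0.5 to 6 h. If recent antipyretic use disqualifies 50 to 80% of readings during fever (again an assumption), the share with a rebound falls from 25–66% to about 11–49%, and the one-reading mean rises to about 73–81 h.

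**The case against.** The strongest reply is that Step 3 shows only that one rule is earlier than a stricter one. It does not show that the one-reading rule is wrong. Under the same assumptions, the underlying mean temperature crosses 37.4 °C on average at 24 × (1.1/0.4) × ln 3 = 72.5 h. Against that target the one-reading means are off by +2.6, −4.7, −1.3 and −7.9 h, and the three-reading means are late by 9.5, 16.7, 11.8 and 16.6 h. The sustained rule comes closer only if resolved means that the daily peak is below 37.4 °C (about 79 to 89 h), and the documents do not choose between these targets. This stands. It is why the sustained version belongs beside the protocol-defined estimate and not in its place.

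A reader might also infer that the plan contradicts itself, because it calls temperature normalised only after 48 hours. The documents do not support that. The 48-hour text says when a subject may stop recording. Symptoms are handled in the same way: recording stops after 48 hours at none or mild, while the endpoint needs 21.5 hours. An endpoint shorter than the recording rule is no contradiction.

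Nor are the later readings unused. Diary temperatures are summarised (SAP 5.2.2, Table 14.2.1.1) and listed (Listing 16.2.6.3). The emphasis on relapse in Protocol 10.2.2 concerns the diary symptoms, not measured temperature.

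What the reply leaves untouched is that one reading suffices, that rebound has no stated handling, and that the SAP gives no reason for treating fever and symptoms differently.

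**Conclusion.** The point holds as a gap in the endpoint definition. The first qualifying diary reading ends the clock and nothing later can reverse it. Relative to a sustained rule the reported time is equal or earlier; that follows from the definitions whenever follow-on readings exist.

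The size is not known. About 0 to 24 h is a range over assumed rates of fall, daily swings and reading errors, largely without the antipyretic condition. It should not be read as an estimate of bias in this trial. The consequence is also limited: the primary endpoint is safety, no hypothesis is tested, and neither alpha nor power is affected. What remains uncertain is whether an uncontrolled estimate of a prominent secondary endpoint depends on transient dips. A cheap added analysis would show this.

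**What to change.** Add to SAP 3.3.8 and 5.2.2 a sustained-resolution analysis: time to the first reading below 37.4 °C that meets the 12-hour antipyretic rule and is followed by no reading of 37.4 °C or above for at least 21.5 hours, timed at that first reading. State that a follow-on reading at or beyond 21.5 hours is needed for confirmation, and whether an antipyretic taken within the period breaks it. Censor subjects without confirmation at their last temperature reading, in line with the existing rule.

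Report this beside the protocol-defined single-reading estimate, with the number of subjects in each age group who have a reading of 37.4 °C or above after their single-reading event. Record the addition in SAP 6.

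The cost is SAP wording and programming. No new data are needed for most subjects, because recording is planned to continue until four normal readings. The downsides are a somewhat longer reported time under the sustained rule and the censoring of a few subjects who lack follow-on readings.
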